8.2.2. Estimated Annual Accrual

We anticipate enrolling approximately 250 subjects per year into prospective screening

8.3. Demographic Analysis

Demographics and clinical characteristics will be summarized using means and standard deviations for continuous variables and counts and proportions for categorical variables. ANOVA

(or its nonparametric analog Kruskal-Wallis) for continuous variables and Fisher's exact test for categorical variables will be utilized to compare these characteristics. Demographic characteristics will be summarized in tabular format.

8.4. Final Analysis Plan

All statistical tests will be performed at 5% significance level and confidence interval at 95% level. There will be no adjustment on the levels for multiple testing. There will also be no imputation methods that will be used for missing data. Any viral load <100 (i.e., undetectable) will be replaced by viral load value of 10. Quantitative viral loads will be analyzed based on the log based 10 transformation.

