3.2.2. Secondary endpoints

- Timing of onset of BK viremia (number of days post-transplant)

- Duration of BK viremia
- Incidence of BKVN in the study population
- Dynamics of quantitative measurements of BK viremia over time
- Frequency of donor and recipient-related risk factors for BV viremia, including:
 - a. Donor-derived factors:
 - i. Deceased donor – Standard criteria donor (SCD), Donor after cardiac death (DCD), Expanded criteria donor (ECD)
 - ii. Living donor – related donor or unrelated donor
 - iii. ABO incompatibility
 - iv. Total HLA mismatches
 - v. HLA C7 status
 - vi. Race/ethnicity
 - vii. Sex
 - b. Recipient-derived factors:
 - i. Delayed graft function (DGF), defined as use of dialysis within 7 days of the transplant
 - ii. Cold ischemia time (CIT)
 - iii. Warm ischemia time (WIT)
 - iv. Use of stents
 - v. HLA C7 status
 - vi. Type/intensity of immunosuppression, including corticosteroids
 - vii. Acute rejection
 - viii. Age
 - ix. Race/ethnicity
 - x. Sex
- Frequency of clinical outcomes that are potentially related to BKV infection, including:
 - a. subject death,
 - b. loss of graft function as defined by GFR <10 mL/min/1.73 m²
 - c. development of urinary outlet obstruction
 - d. development of gross hematuria
 - e. development of lymphocele
 - f. acute rejection
 - g. initiation of dialysis
 - h. re-transplantation
 - i. renal biopsies

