4.3. Intensive Sampling Phase

Approximately 40 viremic subjects (up to a maximum of 60) will be asked to participate in more intensive sampling. Those subjects in whom BK viremia is identified (by PCR result demonstrating BK DNA $\geq 10,000$ copies/ml) will be shifted to a more intensive sampling schedule. A review of the informed consent will be initiated by the research staff to confirm the subject's continued willingness and ability to participate in the intensive monitoring phase until resolution of viremia or until another discontinuation event occurs.

Blood and urine specimen collection will occur every 2 weeks, \pm 7 days, until the BK viremia has resolved (or another study termination endpoint is reached). Resolution of BK viremia is defined as PCR becoming negative (or viral load <1000 copies/ml). Start and stop dates for the Intensive Sampling Phase will be defined by the date that the qualifying (initial positive and subsequent negative) blood samples were drawn.

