8.4.2. Secondary Endpoints

The distribution of the time to onset and duration of BKV viremia will be estimated using survival analysis methods such as Kaplan-Meier estimator for a single group. This will provide estimates of the median time to onset or median duration of BKV viremia. To compare different groups and/or determine risk factors, we will use Cox proportional hazard regression model if the proportional hazards assumption is found to be reasonable. Otherwise, we will consider using parametric survival regression models (in particular, accelerated failure time model). Parametric regression models are useful especially in cases where sample sizes are small or when the percent censored is high. This will also be the tool of preference if there will be left-censored subjects, i.e., subjects who at enrollment show evidence of BK viremia. Cox model cannot handle left-censored data.

As with the BKV viremia, incidence of BKVN will be estimated using a 95% confidence interval for single proportion. We will utilize logistic regression to compare groups, or adjust for covariates or determine risk factor.

To investigate the change in the quantitative BK viremia over time and how it is associated with important factors such as the use of immunosuppressive therapy and recipient's demographic and clinical characteristics, we will again use mixed regression modeling for repeated measures.

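### Replacing every viral load below 100 with 10 feeds censored values into the viral-load mixed model as if measured, and can bias slopes and covariate associations in a direction that cannot be known in advance

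*Combined protocol and SAP*

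**What the plan says.** Section 8.4 (Final Analysis Plan) sets the data rule: "Any viral load <100 (i.e., undetectable) will be replaced by viral load value of 10". It also fixes the scale: "Quantitative viral loads will be analyzed based on the log based 10 transformation". On missing data it says "There will also be no imputation methods that will be used for missing data".

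Section 8.4.2 states the use: "To investigate the change in the quantitative BK viremia over time and how it is associated with important factors", the factors being immunosuppressive therapy and recipient characteristics, and the method: "we will again use mixed regression modeling for repeated measures". This serves the secondary endpoint in section 3.2.2, "Dynamics of quantitative measurements of BK viremia over time".

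No censored-data model, alternative constant or sensitivity analysis is described for values below 100. Left-censoring is mentioned once, in section 8.4.2, for subjects already viremic at enrollment in the time-to-onset analysis.

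Under sections 4.3 and 4.4, subjects enter intensive sampling at 10,000 copies/ml or more. They are sampled every 2 weeks until PCR is negative or below 1000, then about every 4 weeks for 6 months. About 40 viremic subjects are expected, 60 at most.

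**The concern.** A result below 100 carries one piece of information: the load is under 2.0 log10. The rule turns this into a measured 1.0. The mixed model then sees a sudden drop at the limit and a flat line after it. The drop steepens a fitted slope and the floor flattens it; which wins depends on how many values fall below the limit and when.

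This design is exposed because sampling continues for 6 months after resolution, when values below 100 are likely to be common. At stake is whether the reported speed of viral decline, and its association with immunosuppression and recipient factors, reflects the virus or the constant 10. With about 40 viremic subjects, there is little signal to spare.

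**Working it through.** **1. The plan's own figure.** No power or precision is stated for viral-load slopes. The nearest stated figure is the GFR comparison in section 8.2.1 (difference 5.9, SD 10.9, 40 vs 410, 90% power). SE = 10.9 × √(1/40 + 1/410) = 1.806; power = Φ(5.9/1.806 − 1.96) = 0.90. It reproduces, and it does not depend on the viral-load rule.

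**2. The shift made by the rule.** Recorded value = log10(10) = 1.0; limit = log10(100) = 2.0. Shift = 1.0 − log10(true value).

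| True copies | log10 | Shift |
|---|---|---|
| 99 | 1.996 | −0.996 |
| 50 | 1.699 | −0.70 |
| 25 | 1.398 | −0.40 |
| 10 | 1.0 | 0 |
| 5 | 0.699 | +0.30 |
| 1 | 0 | +1.00 |

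A true change of −0.004 (100 to 99) is recorded as −1.00, and no recorded value can lie between 1.0 and 2.0.

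**3. Slope in one group.** The documents give no viral-load mean, slope or SD, so all inputs here are assumptions: start 4.5 log10, between-subject SD 0.6, slope SD 0.15, residual SD 0.4, evenly spaced visits, straight-line decline. Slopes are averaged within-subject least-squares slopes. Entries are the bias after substitution with 10 (plus = too steep), with the share of values below 100 in brackets.

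| True slope (log10/month) | 3 months | 6 months | 9 months |
|---|---|---|---|
| −0.3 | +2% (1%) | +5% (7%) | −2% (19%) |
| −0.5 | +4% (3%) | +1% (22%) | −22% (41%) |
| −0.7 | +7% (9%) | −14% (39%) | −44% (57%) |
| −1.0 | +5% (23%) | −40% (57%) | −66% (70%) |

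The far corner is not realistic: 4.5 − 1.0 × 9 = −4.5 log10. Where the average line ends at 0 log10 (1 copy) or higher, which covers all 3-month cells, 6 months down to −0.7 and 9 months down to −0.5, the range is +7% to −22%.

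**4. Slope difference between two groups** (same inputs, first group −0.4).

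| Second group | 3 months: full / with 10 | 6 months | 9 months |
|---|---|---|---|
| −0.4 | 0 / 0 | 0 / 0 | 0 / −0.002 |
| −0.6 | −0.196 / −0.216 | −0.202 / −0.153 | −0.203 / −0.046 |
| −0.8 | −0.395 / −0.440 | −0.401 / −0.201 | −0.402 / −0.021 |

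Groups with the same distribution show no false difference. Otherwise the result runs from 11% inflated (0.440/0.395) to almost wholly lost. Equal slopes of −0.5 with baselines of 4.2 and 5.2 give spurious differences of +0.03, −0.03 and −0.09 log10/month at 3, 6 and 9 months.

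**5. Left-censored mixed model on the same data.** 20 vs 20 subjects, 6 months, 40 simulated data sets per scenario, random intercept, no random slope.

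| Scenario | Quantity | Full data | With 10 | Censored at 2.0 |
|---|---|---|---|---|
| Slopes −0.4 vs −0.8 | difference | −0.398 | −0.196 | −0.399 |
| Slopes −0.4, baselines 4.2 vs 5.2 | difference | −0.003 | +0.027 | −0.004 |
| Same | slope, first group | −0.397 | −0.439 | −0.396 |
| Slopes −0.5, same baseline | slope | −0.500 | −0.536 | −0.499 |

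Without random slopes the steepening can exceed the 7% of step 3: 0.439/0.397 = 1.11.

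**6. The protocol's sampling scheme.** A mixed-model simulation with 20 vs 20 subjects and 23–32% of values below 100 gave:

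| True difference (log10/week) | With 10 | Censored at 2.0 |
|---|---|---|
| −0.060 | −0.018 | −0.063 |
| −0.040 | −0.022 | −0.038 |

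When the true load levelled off at 1 or 10 copies, the censored model still recovered the decline-phase difference (−0.060 and about −0.04). At about 32 copies it did so less fully (−0.042 and −0.034).

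**The case against.** The strongest reply is that a straight decline continued for months after clearance is the wrong yardstick. With true slopes of −0.10 and −0.16 log10/week on the protocol's sampling, the faster group's mean true value at the last visit is −0.93 log10, about 0.1 copy/ml. A plateau after clearance may be real. If the true load levels off, whole-period slope differences from uncensored data compare with the substituted ones as follows: 0.045 vs 0.017 (plateau at 1 copy), 0.021 vs 0.017 (10 copies), 0.013 vs 0.016 (about 32 copies). The loss can thus be large, about 20%, or absent. This stands, and it rules out any single headline loss. A reader might infer from one straight-line scenario that two thirds of any slope difference disappears; the documents give no trajectories that would support this.

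Four other stronger readings also fail.
- One log is not the error in every undetectable value; it is the shift for true values just under 100.
- The mixed model does not treat these values as error-free, since every observation has residual error. The fault is that censored values count as observed.
- The constant 10 is not shown to be worse than 50. For −0.4 vs −0.8 at 6 months, 50 leaves −0.114 of −0.401, and 10 leaves −0.201.
- The primary endpoint is not at risk. Quantitation of viral load is named in the first primary objective (section 3.1.1), but the only primary endpoint in section 3.2.1 is incidence.

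It can also be said that section 8.4.2 does not commit to a linear slope. Visit means do not escape, though. With a share p of values below 100 at a visit, using 50 in place of 10 moves the mean by 0.70 × p: 0.17, 0.35 or 0.52 log10 for assumed p of 0.25, 0.50 or 0.75.

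**Conclusion.** The concern holds, within limits. A stated rule puts left-censored values into a model that takes them as observed, and the plan has no check on the result. Viral-load slopes and their covariate associations can be biased, and neither direction nor size can be predicted from the documents.

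Under the assumed grid, single-group slope bias runs from about +7% to −66%, or +7% to −22% if the average line is not allowed below 1 copy. Slope differences run from slightly inflated to almost wholly lost, with no group bias when distributions match. These sizes rest on assumed straight-line trajectories and on a model fitted to viremic subjects, a set that section 8.4.2 does not name. That values below 100 will be common is likely from the follow-up scheme, but not stated.

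The scope is the secondary endpoint on viral-load dynamics. Viremia qualifies at 10,000 copies/ml and resolves below 1000, so a rule acting below 100 leaves incidence, onset and duration unchanged; it does not touch GFR. The comparison of site and central PCR results in section 8.4.3 could be affected if the rule is applied there, which the plan does not say.

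**What to change.** In section 8.4, state that values below 100 enter the viral-load mixed model as left-censored at 2.0 log10 (a Tobit-type mixed model), and keep substitution with 10 as a sensitivity analysis.

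The change needs SAP wording only: no new data, visits or subjects. The cost is more complex fitting. The censored model also relies on normality and on the assumed time trend below the limit, where the data cannot check them, with only about 40 viremic subjects. Step 6 shows where this matters: recovery was less complete when the true load levelled off not far below the limit. Reporting both analyses lets a reader see how far the conclusions depend on the treatment of undetectable values.

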8.4.1. Primary Outcome Analysis

Incidence of BK viremia will be estimated using a 95% confidence interval for single proportion. Logistic regression will be used to investigate the risk factors for BKV viremia and BKVN. Factors will include:

- Donor-derived factors:
 1. Deceased donor – Standard criteria donor (SCD), Donor after cardiac death (DCD), Expanded criteria donor (ECD)
 2. Living donor – related donor or unrelated donor
 3. ABO incompatibility
 4. Total HLA mismatches
 5. HLA C7 status
 6. Race/ethnicity
 7. Sex
- Recipient-derived factors:
 1. Delayed graft function (DGF), defined as use of dialysis within 7 days of the transplant
 2. Cold ischemia time (CIT)
 3. Warm ischemia time (WIT)
 4. Use of stents
 5. HLA C7 status
 6. Type/intensity of immunosuppression, including corticosteroids
 7. Acute rejection
 8. Age
 9. Race/ethnicity
 10. Sex

To compare the change in GFR over time between those with and without BKV viremia, we use all available GFR data from each subject. We will use mixed model for repeated measures to analyze the GFR data over time. This analysis method will allow us to use any of the available GFR data

even if they are not complete. We will determine the appropriate covariance structure to use as indicated by the Akaike Information Criterion.

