WHO	World Health Organization

PROTOCOL SUMMARY

- Title:** Natural History of Infection Caused by BK Virus (and other Opportunistic Viral Pathogens) in Renal and Renal-Pancreas Transplant Recipients
- Phase:** Not Applicable (Natural History Study)
- Study Population:** Male and female renal or renal-pancreas transplant recipients at risk for BK virus infection
- Sample Size:** Approximately 450 subjects will be enrolled for screening for BK viremia (15% over-enrollment allowed, to a maximum of 518 screened subjects) to allow identification of approximately 40 (to a maximum of 60) subjects with viremia.
- Number of Sites:** Approximately 6
- Study Duration:** 3 years
- Subject Participation Duration:** Maximum of 24 months
- Objectives:**
- Primary Objectives:**
- To establish the natural history of BK viremia in a multicenter population of renal and renal/pancreas transplant patients, to include incidence, time to onset, duration, and quantitation of viral load;
 - To assess associations between BK viremia and decline in GFR in renal transplant recipients.
- Secondary Objectives:**
- To define the donor and recipient-related risk factors for BK viremia and BKVN in a multicenter population of renal and renal-pancreas transplant patients;
 - To define the frequency of clinical outcomes that are potentially related to BKV infection.
- Tertiary (Exploratory) Objectives:**
- To compare quantitative measurements of BKV DNA by PCR in plasma and (when appropriate) in urine, in order to determine biologic significance;
 - To assess plasma for evidence of other opportunistic viral pathogens, including CMV, EBV, HHV-6, and adenovirus;
 - To assess urine for evidence of other opportunistic viral pathogens, including CMV and adenovirus;

- To compare quantitative BKV PCR results from each site (local or reference laboratory) with matched results from the Central Unit laboratory;
- To explore the potential of biomarkers of tubular injury for predicting increased risk of BKVN;

[figure not shown]
Description of Study Design:

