7.4. Dosing of Immunosuppressive Drugs

Immunosuppressive (IS) drug selection and doses will be determined by the site physicians/investigator in accordance with best clinical practice and local treatment standards. Modification of immunosuppressive drug dosing in response to documented BK viremia (or other indications) may be performed at the discretion of the treating physicians/investigator. All doses and dose changes should be documented in the concomitant immunosuppressive medications section of the eCRF. Failure to document concomitant medication information will be reported as a protocol deviation during screening/surveillance and intensive monitoring periods.

Measurements of immunosuppressive drug levels are not a protocol requirement. However, IS levels that are obtained for standard-of-care medical management during the study will be recorded on the eCRF.

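### Immunosuppression is chosen site by site, but no risk-factor or GFR model includes site, so centre differences could be mistaken for regimen effects or bias the viremia contrast

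*Combined protocol and SAP*

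**What the plan says.** - **Sites.** The Protocol Summary plans about six.
- **Who sets the regimen.** Section 7.4: "Immunosuppressive (IS) drug selection and doses will be determined by the site physicians/investigator in accordance with best clinical practice and local treatment standards". Changes after viremia "may be performed at the discretion of the treating physicians/investigator".
- **Logistic models (8.4.1).** "Logistic regression will be used to investigate the risk factors for BKV viremia and BKVN". Seven donor and ten recipient factors follow. They include stent use and "Type/intensity of immunosuppression, including corticosteroids". Site is not among them.
- **GFR model (8.4.1).** "We will use mixed model for repeated measures to analyze the GFR data over time". No site term and no covariates are named.
- **Survival models (8.4.2).** "To compare different groups and/or determine risk factors, we will use Cox proportional hazard regression model", with accelerated failure time models as the alternative. Site is not named. For BKVN the section allows adjustment for covariates without saying which.
- **Elsewhere.** The viral-load model in 8.4.2 and the regression models in 8.4.3 do not name site. Sites enter the planned analyses only in the PCR reproducibility comparison in 8.4.3.

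**The concern.** The plan makes site a determinant of an exposure that it then tests as a risk factor. If viremia incidence also differs between sites, for whatever reason, site confounds the regimen comparison. A regimen used mainly at high-incidence centres would look harmful even if it had no effect within any centre. The same could happen with any other factor that follows centre practice. Stent use may be one, although the documents do not say so. Ignoring site also makes intervals too narrow for factors that vary mainly between sites.

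Defining risk factors in a multicenter population is the first secondary objective (3.1.2), and the results are meant to identify high-risk groups for later therapeutic studies (Section 4). The association of viremia with GFR decline is a primary objective (3.1.1). Section 8.4 makes no multiplicity adjustment, so nothing else in the plan restrains false positives.

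**Working it through.** **1. The plan's own GFR figure (8.2.1).** The inputs are 40 viremic and 410 non-viremic subjects, SD 10.9, difference 5.9 and two-sided 5%.

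SE = 10.9 × √(1/40 + 1/410) = 1.806. Power is 90.5% by the normal approximation and 90.3% by the noncentral t with 448 df. The stated 90% reproduces. The detectable difference at 90% power is 5.87 by the t-test. This calculation contains no site term.

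**2. Viremia and a regimen with no true effect.** The documents do not give regimen use or viremia rates by site, so everything here is assumed: six sites of 75 (450 in all), three with viremia rate p₁ and regimen share q, three with rate p₂ and share 1 − q.

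Expected rate on the regimen = q·p₁ + (1 − q)·p₂. Expected rate off it = (1 − q)·p₁ + q·p₂.

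For p₁ = 12%, p₂ = 8%, q = 0.8:
- on: 0.8 × 0.12 + 0.2 × 0.08 = 0.112
- off: 0.2 × 0.12 + 0.8 × 0.08 = 0.088
- spurious odds ratio: (0.112/0.888) / (0.088/0.912) = 1.31

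Simulated rejection rates at nominal 5% (pooled chi-square versus Cochran-Mantel-Haenszel stratified by site):

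| Assumed site pattern | Site ignored | Stratified |
|---|---|---|
| 12% vs 8%, use 80/20, aligned | 13–14% | 5% |
| Rates 6–16% and use 20–80%, rising together | 16–17% | 5% |
| 12% vs 8%, use 60/40, aligned | about 6% | 5% |
| 16.6% vs 6%, use 80/50/20 within each group of three (not aligned) | 5% | 5% |
| 16.6% vs 6%, use 80/20, aligned (outer bound) | 57–58% | 5% |

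**3. Without building alignment in.** Here site rates vary at random on the logit scale around 10%, and the regimen pattern is unrelated to them, so alignment arises only by chance. False-positive rates with site ignored (4,000 runs each):

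| Between-site logit SD | Regimen wholly set by site | 90:10 by site | Mixed use, 20–80% |
|---|---|---|---|
| 0 | 4% | 5% | 5% |
| 0.3 | 12% | 10% | 5% |
| 0.5 | 24% | 17% | 8% |
| 0.7 | 36% | 28% | 12% |

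Stratified by site, the rate is 4.6–5.6% wherever the regimen varies within sites. Where it is wholly set by site, the stratified test has no information.

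**4. GFR contrast.** Take the outer-bound rates of 16.6% and 6%. The share of viremic subjects at the high-rate sites is 0.166/(0.166 + 0.06) = 0.735. For non-viremic subjects it is 0.834/(0.834 + 0.940) = 0.470. The difference is 0.264. If mean GFR change differs by d between the two groups of sites, the viremia contrast is biased by 0.264·d. For d = 2, 5 or 10 ml/min/1.73 m² (assumed), that is 0.5, 1.3 or 2.6, against the plan's detectable 5.9.

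**5. Cost of a site term in the GFR comparison.** Five fixed site terms leave the detectable difference at 5.87 if viremia is balanced over sites. With 16.6%/6% rates the variance rises by a factor of 1.03. The detectable difference becomes about 5.95, and power at 5.9 is about 89.5%.

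**6. Room in the logistic model.** Some 40 events over 17 listed factors is 2.4 events per factor, counting each as one parameter. With five fixed site terms it is 40/22 = 1.8.

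**The case against.** **The size is assumed.** This stands. The large figures need regimen use and viremia rates to line up by site. With weak or no alignment the error rate stays near 5–6%. No document shows which pattern applies.

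**Table 1 does not show that centres differ.** This also stands. A reader might infer from its 6% to 16.6% that the trial's sites will differ that much, and so adopt the 57–58% error rate. The table lists separate published studies from three countries, some small, with mixed designs. With counts rounded from its percentages (23/200, 19/156, 11/66, 7/120, 21/134), the heterogeneity chi-square is 7.45 on 4 df, p = 0.11. The range serves only as an assumed outer limit.

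**Detection is largely common.** A reader might infer that viremia detection varies by site, because a local PCR can qualify a subject (4.2). Sections 6.1, 6.2 and 7.5 send a plasma specimen to the central laboratory at enrollment and every screening visit, to be assayed in real time. Every screened subject therefore has central testing, and the point should not rest on detection.

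**The GFR model names no regimen term.** Centre differences there cannot be read as regimen effects. Only the viremia contrast can be biased.

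**The list is not closed.** The wording in 8.4.1 and the reference to covariates in 8.4.2 do not exclude site. But leaving site to be chosen after the data are seen is the gap that pre-specification should close.

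**Adjustment has a price.** Stratifying discards the between-site regimen contrast. The within-site contrast that remains may be confounded by indication. This stands as a limit on what any site-adjusted estimate can claim. It does not justify ignoring site.

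**Conclusion.** The concern holds in conditional form. Sites choose the regimen, the regimen is a tested risk factor, and no planned risk-factor or GFR model accounts for site. If regimen use and outcome both differ by site, the risk-factor results could mistake centre for regimen or other centre practice, and the GFR contrast could be biased.

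A moderate assumed pattern (12% vs 8%, use 80/20, aligned) gives a spurious odds ratio of 1.31 and about 13–14% false positives, against 5% with stratification. The documents do not support saying that this bias will occur, or that it will be as large as the Table 1 range would imply.

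The sole listed primary endpoint, incidence of viremia (3.2.1), is not the target of this point. What is affected is the first secondary objective and, through the GFR model, one of the two primary objectives. The plan should be changed, because the omission is clear and the correction is cheap.

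**What to change.** In 8.4.1 and 8.4.2:

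- Pre-specify site as a stratum or random intercept in the logistic models for viremia and BKVN and in the Cox or accelerated failure time models. Given the event count, avoid adding fixed site coefficients to the full factor list. The 5% error rates above were computed for stratification; a random intercept was not simulated.
- Include a site effect, fixed or random, in the GFR mixed model. Site-by-time terms are not required.
- Tabulate regimen and stent use by site, so that readers can see how much within-site information exists.
- State that immunosuppression and stent effects are estimated with site accounted for, and report any factor that does not vary within sites as not estimable within site.

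**Cost.** Only analysis-plan wording changes, since site is known for every subject. Some intervals will widen. Sites with no events or a single regimen will contribute little, which matters most for BKVN. Confounding by indication within sites remains and should be stated as a limitation.
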